3.2.1.6 Pruritus Categorical Scale (PCS)

The 4-point PCS is used by the subjects to report the intensity of their pruritus. The scale ranges from 0 (absence of pruritus) to 3 (severe pruritus). Subjects will record their PCS scores on an electronic device, and will complete the assessment once daily in the evening throughout the clinical trial (including the run-in and the follow-up period).

Weekly prorated average score will be calculated. When used in analysis on proportion of subjects achieving PCS success (e.g., PCS ≤ 1), the calculated scores will be rounded to 1 before the determination of responder status. If a subject has less than 4 diary entries in a week, the

weekly average scores will be set to missing. Refer to Section 4.2 for classification of diary data into analysis week/visit.

3.2.1.7 Dynamic Pruritus Score (DPS)

The 9-point DPS is a dynamic scale to be used by subjects to evaluate the change of their pruritus compared with an earlier time point (i.e., before injection on day 1). The scale ranges from 0 (strongly worsened pruritus) to 8 ([almost] no pruritus anymore), including intermediate marks for slightly improved/worsened, moderately improved/worsened, and rather improved/worsened. Subjects will record their DPS score on an electronic device, and will complete the assessment 2, 4, 8, 24, 48 and 72 hours after study drug injection on day 1.

3.2.1.8 5-D itch scale

The 5-D itch scale is a multidimensional measure of itching that has been validated in subjects with chronic pruritus. The 5 dimensions included in the scale are duration, degree, direction, disability and distribution. The scores for each of the 5 domains are achieved separately and then summed together to obtain a total 5-D score, which ranges between 5 (no pruritus) to 25 (most severe pruritus). At a given visit, there must be responses to at least 3 out of 5 domains. If fewer than 3 responses, then the total 5-D score will be set to missing.

The duration, degree and direction domains are single-item domain.

The score for the disability domain is achieved by taking the highest score on any of the 4 items. The disability score is missing when scores for all 4 items are missing.

For the distribution domain, the number of affected body parts is tallied (potential sum 0-16) and the sum is sorted into 5 scoring bins as follows:

- sum of 0-2 = score of 1
- sum of 3-5 = score of 2
- sum of 6-10 = score of 3
- sum of 11-13 = score of 4
- sum of 14-16 = score of 5

The 5-D itch scale will be administered at baseline and week 2.

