3.2.6.2 Hospital Anxiety and Depression Scale (HADS)

HADS is a validated questionnaire containing 14 items, 7 each for anxiety and depression. Subject will rate each question ranging from 0 to 3, and the total score ranges from 0 to 21 for each sub-scale. HADS will be administered only to the subset of subjects who fluently speak a language in which the questionnaire is presented.

For each sub-scale, the score will be categorized as follows:

- 0-7 = Normal
- 8-10 = Borderline abnormal (borderline case)
- 11-21 = Abnormal (case):

HADS will be assessed at baseline, weeks 12, 24, or early termination visit when applicable.

At a given visit, there must be responses to at least 6 out of 7 questions within each sub-scale of anxiety and depression. If fewer than 6 responses, then the sub-scale will be set to missing.

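### The SAP accepts partial 5-D itch and HADS forms without prorating them; as written the 5-D total is biased low, and the HADS rule for a missing item is not stated

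*SAP*

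**What the plan says.** **5-D itch (SAP 3.2.1.8).** The total is an addition: "The scores for each of the 5 domains are achieved separately and then summed together to obtain a total 5-D score". The section puts the lowest possible total at 5, meaning no itch, and the highest at 25. A partial form is accepted: "At a given visit, there must be responses to at least 3 out of 5 domains". Below that it is dropped: "If fewer than 3 responses, then the total 5-D score will be set to missing". Nothing says what stands in for one or two unanswered domains. Protocol 7.1.1.8 also says only that the domain scores are added up.

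**HADS (SAP 3.2.6.2).** The scale is described by its range: "Subject will rate each question ranging from 0 to 3, and the total score ranges from 0 to 21 for each sub-scale". The completeness rule is that "there must be responses to at least 6 out of 7 questions within each sub-scale of anxiety and depression"; with fewer, the sub-scale is missing. The section does not say how items are combined or how one missing item is handled, and Protocol 7.5.2 adds nothing.

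**Use.** The change in 5-D total at week 2 is analysed by ANCOVA (SAP 4.7.4.9). HADS sub-scores are analysed by MMRM, and the proportion at 11 or above by a CMH test (SAP 4.9.3.2).

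**Where the SAP does give a rule.** Diary scores are prorated (SAP 3.2.1.5, 3.2.1.6 and 3.2.1.9). One blank DLQI question scores 0, and two or more blanks void the form (SAP Appendix 3). Question-level LOCF and WOCF (SAP 4.7.1.3) belong to sensitivity analyses of the primary and selected secondary endpoints. SAP 3.2.2.2 names the latter as IGA, EASI and peak pruritus NRS, so neither 5-D nor HADS is covered.

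**The concern.** A threshold of 3 of 5 or 6 of 7 exists only so that partial forms can be scored. Every 5-D domain contributes at least 1 point, so adding up only the answered domains must give a lower total than the complete form would have given. That total then counts as observed, and neither the ANCOVA nor the MMRM can correct it.

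At stake are the change in 5-D total at week 2 and, if HADS items are added in the same way, the HADS change scores and the count of subjects at or above the case cut-off of 11.

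**Working it through.** **Inputs.** 5-D: five domains, each scored 1 to 5, added; minimum 3 answered (SAP 3.2.1.8, form in Protocol Appendix 8). HADS: seven items per sub-scale, each 0 to 3; minimum 6 answered; integer bands 0–7, 8–10 and 11–21 (SAP 3.2.6.2); analysis cut at 11 (SAP 4.9.3.2).

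**1. Stated ranges reproduced.** 5-D: 5 × 1 = 5 to 5 × 5 = 25. HADS: 7 × 0 = 0 to 7 × 3 = 21. Both agree with the SAP for complete forms.

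**2. 5-D with k answered domains.** The sum runs from k to 5k: 4 to 20 for k = 4, and 3 to 15 for k = 3. Totals of 3 and 4 are outside the SAP's own range.

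**3. A subject unchanged at 3 on every domain.**
- Complete: 5 × 3 = 15.
- One domain missing: 4 × 3 = 12, a change of −3 (−20%).
- Two missing: 3 × 3 = 9, a change of −6 (−40%).
- Largest possible artefact: −5 for one domain, −10 for two.
- Direction, one domain missing: gap at week 2, 12 − 15 = −3 (false improvement); gap at baseline, 15 − 12 = +3 (false worsening); same gap at both visits, 12 − 12 = 0.

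**4. Which 5-D domains can be missing.** Distribution is a tally of ticked body parts, and 0 to 2 parts scores 1, so a blank list scores 1 and is not missing. Disability takes the highest of four items, and "The disability score is missing when scores for all 4 items are missing"; one skipped item lowers it only if that item was the highest. A gap therefore has to come from duration, degree, direction or a wholly blank disability block.

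**5. HADS, if the six answered items are summed (an inference).** The range becomes 0 to 6 × 3 = 18, and the largest loss is 3. A subject at 2 on every item goes from 14 to 12. At the cut-off: 11 − 1 = 10, 12 − 2 = 10, 13 − 3 = 10. Each subject leaves the group at 11 or above with no change in state.

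**6. Group effect on 5-D.** The documents give no rate of partial forms, so these are assumptions: 2%, 5% or 10% of week-2 forms lack one domain.
- Mean of one arm, mean domain score 3: −0.02 × 3 = −0.06, −0.05 × 3 = −0.15, −0.10 × 3 = −0.30.
- Difference between arms, equal rates, mean domain scores 2.5 and 3.5: the true difference is 5 × (3.5 − 2.5) = 5 points. The artefact is rate × (3.5 − 2.5) = 0.02, 0.05 or 0.10 points towards zero, that is 0.4%, 1% or 2% of the difference.

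**7. Effect of proration.** 5-D: 12 × 5/4 = 15 and 9 × 5/3 = 15, so the unchanged subject keeps 15, and the range returns to 5–25. HADS: 12 × 7/6 = 14; 10 × 7/6 = 11.67, which stays at or above 11. But 9 × 7/6 = 10.5 falls between the 8–10 and 11–21 bands, so a rounding rule is needed.

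**The case against.** The strongest reply is that the SAP never says that a partial form is to be scored as a bare sum. For HADS this is right: no method of combination is given, so the defect there is an unstated rule, and step 5 shows only what the obvious reading would do. For 5-D it is weaker. The section says to add, says when to add and gives no other step. That the result can leave the stated range shows that the rule is incomplete; it does not supply another one.

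A reader might infer that the rule favours nemolizumab. The documents do not support this. The direction depends on which visit has the gap, and with equal missingness the difference between arms shrinks slightly. A reader might also take a shift of 0.15 or 0.30 points as bias in the treatment effect. Those are one-arm figures at assumed rates, and most of the shift cancels when the arms have similar missingness.

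Exposure may also be small. Two missing 5-D domains is hard to reach (step 4). HADS is collected on an electronic device (Protocol 10.3), which might prevent skipped items, though the documents do not say so. 5-D is not in that list, so the same comfort cannot be assumed for it.

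Proration has a cost too. It treats the answered domains or items as representative of the missing one. A subject with a six-item HADS sum of 10 whose skipped item would have scored 0 has a true score of 10 and would be prorated to 11.67, a false case. This stands as a limitation, but it is an error that can go either way, whereas a bare sum can only lower the score.

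**Conclusion.** The point holds, at low severity. For 5-D, the rule followed as written biases a partial total downwards: it can give 3 or 4 on a scale that starts at 5, and it moves an unchanged subject at 15 to 12 or 9. For HADS, the treatment of the one permitted missing item is not specified. If the items are simply summed, the loss is up to 3 points and can take a subject at 11, 12 or 13 out of the case group.

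The effect on the treatment comparison cannot be sized from the documents, because the rate of partial forms and its balance across arms are unknown. Under the assumed equal rates of 2% to 10%, it is a dilution of 0.02 to 0.10 points on a 5-point difference.

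The effect is confined to an endpoint in the SAP's list of other efficacy endpoints and to a quality-of-life measure given only to subjects fluent in an available language version. The primary endpoint, the selected secondary endpoints and the sample size are untouched.

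**What to change.** Add a scoring rule to each section before database lock:

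- **SAP 3.2.1.8:** when at least 3 domains are answered, 5-D total = sum of answered domains × 5 / (domains answered).
- **SAP 3.2.6.2:** say that the sub-scale is the sum of its items and that, when at least 6 are answered, sub-scale = sum × 7 / (items answered). Round to the nearest integer before the bands and the cut at 11 are applied, and state which way a half goes: a six-item sum of 9 gives 10.5, and that choice decides case status.

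The alternative is to set any incomplete total to missing. That avoids the representativeness assumption but loses the partial forms that the thresholds were meant to keep.

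The cost is a sentence or two per scale and a small programming change, with no change to data collection. Reporting the number of partial forms by arm and visit would show whether the point mattered.

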3.2.1.9 Sleep Disturbance Numeric Rating Scale (NRS-Sleep)

The sleep disturbance NRS is a scale to be used by the subjects to report the degree of their sleep loss related to AD. Subjects will record their sleep disturbance NRS scores on an electronic device, and will complete the assessment once daily in the morning throughout the clinical trial (including the run-in and the follow-up period).

Weekly prorated average score will be calculated and used in the analysis. If a subject has less than 4 diary entries in a week, the weekly average scores will be set to missing. Refer to Section 4.2 for classification of diary data into analysis week/visit.

3.2.2 Efficacy endpoints

3.2.2.1 Primary endpoint

Percent change from baseline in EASI at week 24

3.2.2.2 Secondary efficacy endpoints

- Proportion of subjects achieving IGA success (defined as IGA 0 [clear] or 1 [almost clear]) at each visit up to week 24
- Proportion of subjects achieving IGA success (defined as IGA 0 [clear] or 1 [almost clear]) and a reduction of ≥ 2 points at each visit up to week 24
- Percent change from baseline in EASI at each visit up to week 24
- Absolute and percent change from baseline in weekly average of the peak and average pruritus NRS at each visit up to week 24
- Proportion of subjects with an improvement of weekly average pruritus peak NRS ≥ 4 from baseline to week 24
- Absolute and percent change from baseline in weekly average sleep disturbance NRS at week 24
- Proportion of subjects achieving PCS success (defined as a weekly prorated rounded average PCS ≤ 1 [none - mild]) at week 24
- Proportion of subjects with EASI-50, EASI-75 or EASI-90 (defined as achieving 50%, 75% or 90% reduction from baseline in EASI score) at each visit up to week 24
- Absolute and percent change from baseline in SCORAD at week 24

The endpoints of IGA, EASI, and peak pruritus NRS are considered as selected secondary efficacy endpoints hereafter.

3.2.2.3 Other efficacy endpoints

- Disease severity scores (EASI, IGA, SCORAD, BSA, pruritus NRS, sleep disturbance NRS and PCS) at each visit including follow up visits (week 28 and 32)
- Change and percentage change from baseline in disease severity scores (EASI, SCORAD, pruritus NRS and sleep disturbance NRS) at each visit
- Change and percentage change in disease severity scores (EASI, SCORAD, pruritus NRS, and sleep disturbance NRS) from week 24/ET to follow up visits (week 28 and 32)
- Proportion of subjects with an improvement of weekly average pruritus NRS ≥ 4 from baseline to each visit
- Proportion of subjects achieving PCS success (defined as a weekly prorated rounded average PCS ≤ 1 [none - mild]) at each visit including follow-up visits
- DPS at hour 2, 4, 8, 24, 48, and 72

- Monthly and total amount of TCS (medium and low potency TCS only) used during the treatment period (baseline to week 24)
- Time to rescue therapy
- Change from baseline in 5-D itch scale total score at week 2
- Prurigo nodularis lesions over time, if applicable

3.2.3 Safety Variables

Safety assessments will be conducted for all subjects at the screening visit (upon the signature of the informed consent form [ICF]) and at every subsequent visit.

Safety assessments include electrocardiogram (ECG), physical examination, vital signs, body weight, respiratory assessments (peak expiratory flow [PEF] measurement only for subjects with a medical history of asthma), laboratory safety tests, and AE recording (including serious AEs [SAE], AEs of Special Interest [AESI] and selected AEs).

3.2.3.1 Electrocardiograms (ECG)

A 12-lead ECG will be performed at screening, baseline, weeks 1, 12, 24, or early termination and/or unscheduled visits when applicable.

All abnormal ECG findings considered to be clinically significant by the investigator at the screening visit will be recorded in the Medical History form. Any clinically significant changes from the screening visit will be reported as AEs in the eCRF.

3.2.3.2 Physical examination and vital signs

Physical examination: The physical examination will be performed at screening, baseline, weeks 1, 2, 4, 8, 12, 16, 20, 24, 28, 32, or early termination and/or unscheduled visits when applicable.

All clinically significant abnormal findings at the screening visit will be recorded in the Medical History form. Any clinically significant changes from the screening visit will be recorded as an AE.

At baseline, investigator or qualified personnel should assess on each subject whether lesions of prurigo nodularis are present or absent. If the lesions of prurigo nodularis are present, investigator needs to evaluate the lesions at each subsequent visit using a 5-point scale (2: very much improved; 1: improved; 0: no change; -1: worsened; -2: very much worsened).

Vital signs: The vital signs will be evaluated at screening, baseline, weeks 1, 2, 4, 8, 12, 16, 20, 24, 28, 32, or early termination and/or unscheduled visits when applicable.

Vital signs will include pulse rate, systolic and diastolic blood pressure (after the subject has been sitting for at least 5 minutes), and body temperature. All abnormal values at the screening

visit identified as clinically significant by the investigator will be recorded in the Medical History form. Any clinically significant changes from the screening visit will be recorded as an AE.

Height and Weight: Height will be measured at the screening visit only, and weight will be measured at screening, baseline, weeks 4, 8, 12, 16, 20 and 24.

Any clinically significant weight changes from the screening visit will be recorded as an AE.

Blood pressure (systolic and diastolic), pulse rate, and weight values meeting criteria for potentially clinically significant values (PCSV) will be reported.

Criteria for PCSV for vital signs and weight are listed in Appendix 2.

3.2.3.3 Respiratory Assessments

At each visit, investigator or designee will perform a respiratory physical examination and ask all subjects whether they have experienced any signs/symptoms of asthma. In addition, for subjects reporting a medical history of asthma, PEF will be performed.

Newly diagnosed asthma or worsening of asthma during the study will be reported as AESI.

3.2.3.4 Laboratory safety tests

The following laboratory safety tests will be performed:

- Hematology: white blood cell (WBC) count with differential count (including eosinophils), red blood cell (RBC) count, hemoglobin (Hb), hematocrit (hct), mean cell volume (MCV), and platelet count (Plt)
- Blood chemistry: sodium, potassium, calcium, chloride, glucose, urea, creatinine, aspartate aminotransferase (AST)/ alanine aminotransferase (ALT), alkaline phosphatase (ALP), total and direct bilirubin, creatinine phosphokinase (CPK), high sensitivity C-reactive protein (hsCRP), fibrinogen, gamma-glutamyl transpeptidase (GGT), lactate dehydrogenase (LDH), total protein, albumin, uric acid, total cholesterol, low-density lipoprotein (LDL), high-density lipoprotein (HDL) and triglycerides
CPK isoenzyme test will be performed only if CPK is elevated to >2.5X Upper Limit of Normal (ULN).
- Urinalysis: blood, proteins, leukocytes, glucose, ketones, nitrites, bilirubin, urobilinogen, pH, and specific gravity

All clinically significant out-of-range laboratory values at the screening visit will be recorded in the medical history form. All clinically significant out-of-range laboratory values after the screening visit are to be reported as an AE if this abnormality was not present at the screening visit or is assessed as having worsened since the screening visit (i.e., changed significantly from the screening visit).

3.2.3.5 Adverse events

Adverse events (AE) will be coded using the Medical Dictionary for Regulatory Activities (MedDRA) version 19.0.

An AE will be considered a treatment-emergent AE (TEAE) if it started after the date of the first dose of study drug or it started before the date of the first dose of study drug and worsened after the date of the first dose. AEs occurring on the date of the first dose of study drug will be considered a TEAE if the onset of the AE is on or after the time of injection on that day. Where dates are missing or partially missing, AEs will be assumed to be treatment-emergent, unless there is clear evidence (through comparison of partial dates) to suggest that the AE started prior to the first dose of study treatment.

The investigator will have to assess if there is a reasonable possibility of a causal relationship between the study drug and/or a study procedure (e.g. injection, TCS, blood sample collection) and an AE. Related AEs will be defined as study drug related AEs or study procedure related AEs.

The AESIs for this clinical trial have been defined as follows:

- Elevated ALT or AST (> 3 ULN) in combination with elevated bilirubin > 2 ULN, whether or not considered as related to the study drug by the investigator
- Newly diagnosed asthma or worsening of asthma
- Elevated CPK (≥ 2.5 ULN) if considered to be related to study drug by the investigator

The following AEs will be considered as selected AEs for this clinical trial:

- Exacerbation of AD: defined as a clinically significant worsening of AD signs and/or symptoms that requires therapeutic intervention (rescue therapy) and that is not considered by the investigator to be a part of the natural course of AD (e.g. change in severity or the nature of the disease). When recording worsening of AD on the AE form in the eCRF, the AE reported term should include an appropriate descriptor (e.g. “worsening of AD” or “AD flare”).
- Injection-related reaction (IRR): defined as any local or systemic reactions (including hypersensitivity) related to the injection, regardless of the time of the AE onset.
- Peripheral edema: defined as swelling of any skin or subcutaneous body tissues (for example legs, hands, etc.) but excluding edema linked to urticaria.
- Skin infection
- Systemic infection
- Headache

Missing date information for AEs

The following imputation rules only apply to cases in which the start date for AEs is incomplete (i.e., partial missing).

Missing Month and Day

- If the year of the incomplete start date is the same as the year of the first administration of the study drug, then the month and day of the first administration of the study drug will be assigned to the missing fields.
- If the year of the incomplete start date is before the year of the first administration of the study drug, *December 31* will be assigned to the missing fields.
- If the year of the incomplete start date is after the year of the first dose of double-blind IP, *January 1* will be assigned to the missing fields.

Missing Month Only

- If only the month is missing, then the day will be treated as missing and both the month and the day will be replaced according to the procedure above.

Missing Day Only

- If the month and year of the incomplete start date are the same as the month and year of the first administration of the study drug, then the day of the first administration of the study drug will be assigned to the missing day.
- If either the year of the incomplete start date is before the year of the date of the first administration of the study drug or if both years are the same but the month of the incomplete start date is before the month of the date of the first administration of the study drug, then the last day of the month will be assigned to the missing day.
- If either the year of the incomplete start date is after the year of the date of the first administration of the study drug or if both years are the same but the month of the incomplete start date is after the month of the date of the first administration of the study drug, then the first day of the month will be assigned to the missing day.

If the stop date is complete and the imputed start date as above is after the stop date, then the start date will be imputed by the stop date.

If the start date is completely missing and the stop date is complete, then the following algorithm will be used to impute the start date:

- If the stop date is after the date of the first administration of the study drug, then the date of the first administration of the study drug will be assigned to the missing start date.
- If the stop date is before the date of the first administration of the study drug, then the stop date will be assigned to the missing start date.

